3.8.3 Statistical Analyses of Adverse Events

AEs will be analyzed according to the body system described in the *CIT-TCAE* manual. Any event that appears in a body system will be categorized into one of the five severity grades according to the *CIT-TCAE* manual or the general definition of severity given in Table 7 and analyzed accordingly. For each event, we will analyze its incidence rate per 100 person-days. Suppose for each subject, the incidence of a particular event is a Poisson process with the homogeneous incidence rate λ . At the time of analysis, if a subject is only followed r days after the randomization, the incidence of this event is distributed according to the Poisson distribution with mean $r\lambda/100$. The maximum

likelihood estimate of the incidence rate will be obtained based on data collected from the available subjects at the analysis time. The 95% confidence interval derived using the maximum likelihood estimator theory will be also reported. The results will be summarized in the table provided in SAP Appendix 4. Moreover, we will also list all the individuals who have ever had an incident of any of the AEs listed in Appendix 5 since their randomization.

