3.8 Safety Analyses

Safety analyses will be conducted for the safety population. Summaries will be prepared for the targeted safety endpoints listed in the secondary endpoints and for all observed AEs organized by body system. The CIT consortium modified the National Cancer Institute (NCI) toxicity table to create a document relevant for trials of adult pancreatic islet transplantation. The resulting reference manual, "Terminology Criteria for Adverse Events (TCAE) In Trials of Adult Pancreatic Islet Transplantation," provides descriptive terminology and a grading (severity) scale which will be utilized for adverse event (AE) reporting.

Regular safety analyses will be prepared for the Data Safety Monitoring Board (DSMB). These summaries will be used to monitor the overall safety profile of the study. These analyses will summarize all AE data that are available at the time of the DSMB meeting. Analyses will summarize AEs by Medra term and body system. Separate incidence summaries will be prepared for serious AEs, for nonserious AEs and for all AEs combined. Separate tables will summarize severity and attribution. Each AE can be attributed to the investigational agent (allogeneic islets), the immunosuppression, both or neither. Identical safety summaries will be included in the final statistical report.

The protocol also describes targeted safety endpoints. The planned analyses for general safety outcomes and for these targeted safety endpoints are described in the following few sections.

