3.8.2 Analysis of Secondary Endpoints for Safety

The safety secondary endpoints in this study target AEs related to islet transplantation (transplant procedure and/or islet product) and the immunosuppression and/or infection prophylaxis.

The targeted AEs related to the islet transplantation include:

1. AE-IIP-1: Bleeding (>2 g/dL decrease in hemoglobin concentration)
2. AE-IIP-2: Segmental portal vein thrombosis
3. AE-IIP-3: Biliary puncture
4. AE-IIP-4: Wound complication (infection or subsequent hernia)
5. AE-IIP-5: Increased transaminase levels (>5 times ULN)

The targeted AEs related to the immunosuppression and infection prophylaxis therapy include:

1. AE-IP-1: Allergy
2. AE-IP-2: Reduction in GFR
3. AE-IP-3: Increase in urinary albumin excretion
4. AE-IP-4: Addition or intensification of anti-hypertensive therapy
5. AE-IP-5: Addition or intensification of anti-hyperlipidemic therapy
6. AE-IP-6: Oral ulcers
7. AE-IP-7: Lower extremity edema
8. AE-IP-8: Gastrointestinal toxicity
9. AE-IP-9: Neutropenia, Anemia, or Thrombocytopenia
10. AE-IP-10: Viral, Bacterial, or Fungal Infections
11. AE-IP-11: Benign or Malignant Neoplasms

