Appendix 4 - Analysis of Adverse Events at Month # since the Randomization

	AE related to the islet transplantation (islet product or islet transplant procedure) or immunosuppression and/or infection prophylaxis			AE not related to the islet transplantation (islet product or islet transplant procedure) or immunosuppression and/or infection prophylaxis		
All Adverse Events	# of incidences	The incidence rate per 100 person- days (λ)	The 95 % confidence interval of λ based on MLE theory	# of incidences	The incidence rate per 100 person- days(λ)	The 95 % confidence interval of λ based on MLE theory
Body System A 1. Grade 5 2. Grade 4 Event 1 Event 2 ⋮ 3. Grade 3 Event 1 Event 2 ⋮ 4. Grade 2 Event 1 Event 2 ⋮ 5. Grade 1 Event 1 Event 2 ⋮						
Body System B 1. Grade 5 2. Grade 4 Event 1 Event 2 ⋮ 3. Grade 3 Event 1 Event 2 ⋮ 4. Grade 2 Event 1 Event 2 ⋮ 5. Grade 1 Event 1						

Event 2 ⋮						
Body System C 1. Grade 5 2. Grade 4 Event 1 Event 2 ⋮ 3. Grade 3 Event 1 Event 2 ⋮ 4. Grade 2 Event 1 Event 2 ⋮ 5. Grade 1 Event 1 Event 2 ⋮						
⋮						

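### Appendix 4 divides events that arise only around an islet infusion by all person-days since randomization, so the printed rate falls as follow-up lengthens even when procedural risk is unchanged

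*SAP*

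**What the plan says.** SAP section 3.8.3 covers all adverse events, by body system and severity grade. It states: "For each event, we will analyze its incidence rate per 100 person-days". The model is a "Poisson process with the homogeneous incidence rate" λ. The exposure is fixed by the clause "if a subject is only followed r days after the randomization", for which the expected count is rλ/100. The maximum likelihood estimate and a 95% interval from likelihood theory go into Appendix 4.

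Appendix 4 is titled "Analysis of Adverse Events at Month # since the Randomization", with the month left open. Its first column group is "AE related to the islet transplantation (islet product or islet transplant procedure) or immunosuppression and/or infection prophylaxis"; its second is for events unrelated to any of these. Each group has a count, a rate per 100 person-days and an interval. Neither section 3.8.3 nor Appendix 4 gives an at-risk window around an infusion or counts infusions in a denominator.

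Section 3.8.2 shows what kind of events the first group contains. Its list for islet transplantation includes "AE-IIP-3: Biliary puncture", "AE-IIP-2: Segmental portal vein thrombosis" and bleeding. Section 3.1.1 allows up to three transplants, the last no later than 8 months after the first, followed by 24 months of follow-up after the final one. Section 3.8 adds, for the regular DSMB reports: "These analyses will summarize all AE data that are available at the time of the DSMB meeting". The same summaries go into the final statistical report.

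**The concern.** A constant daily hazard suits an event that can happen on any day of follow-up, such as an infection under continuing immunosuppression. It does not suit a biliary puncture or a procedural bleed, which can occur only around an infusion. Once infusions have stopped, each further day adds to the denominator and cannot add to the numerator. The estimate then describes how long subjects have been followed rather than how risky the procedure is.

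Two things are at stake. Tables cut at different average follow-up are not comparable for these events, and a falling rate could be mistaken for improving procedural safety. The printed interval also narrows around a value that has no stable meaning. Section 1 of the SAP sets out to show that benefit justifies the risks of the procedure and of the immunosuppression, so procedural risk should be shown on a scale that a reader can interpret.

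**Working it through.** **Inputs.** 48 subjects (section 2.1). Six subjects with the bleeding event AE-IIP-1, which is the template entry in Appendix 3 and not trial data. Up to three infusions, the last within 8 months of the first (section 3.1.1). A second infusion is considered at 75 ± 5 days (section 3.1.1). The cut-offs at Days 75, 180, 365 and 730 are illustrative, since Appendix 4 names no month.

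**Reproducing the SAP's figure.** 6/48 = 12.5%, as printed in Appendix 3. The SAP prints no person-day rate to reproduce.

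**Rate under section 3.8.3.** With mean rλ/100 per subject, the maximum likelihood estimate is λ = 100 × events / Σr. The Wald interval is λ ± 1.96 × 100 × √events / Σr. Assume one infusion per subject, all six events soon after it, and complete follow-up to the cut-off:

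| Cut-off | Person-days | Rate per 100 person-days | 95% interval | Percentage of subjects |
|---|---|---|---|---|
| Day 75 | 48 × 75 = 3,600 | 0.167 | 0.033 to 0.300 | 12.5% |
| Day 180 | 48 × 180 = 8,640 | 0.069 | – | 12.5% |
| Day 365 | 48 × 365 = 17,520 | 0.034 | 0.007 to 0.062 | 12.5% |
| Day 730 | 48 × 730 = 35,040 | 0.017 | 0.003 to 0.031 | 12.5% |

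The fall is 365/75 = 4.87-fold by Day 365 and 730/75 = 9.73-fold by Day 730. The Day 75 interval starts at 0.033 and the Day 730 interval ends at 0.031, so the same six events give two intervals that do not overlap.

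**Test of the constant-hazard assumption.** If the Day 75 rate held, the further events expected by Day 730 would be (6/3,600) × 48 × 655 = 52.4. For an event tied to the infusion, with no further infusion, none would occur.

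**Repeat infusions.** Let each infusion carry the same risk, let m be the mean number of infusions per subject, and let only the first fall before Day 75. Events by Day 730 are then 6m, and the fall is 730/(75m):

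| m | Fall, Day 75 to Day 730 |
|---|---|
| 1 | 9.7-fold |
| 1.5 | 6.5-fold |
| 2 | 4.9-fold |
| 3 | 3.2-fold |

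The SAP gives no expected m.

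**Time from randomization to therapy.** Subjects are randomized once a pancreas is available (section 3.3.1), and therapy starts on Day -2 (section 3.1.1). Adding 2 days to each r changes 9.73-fold to 732/77 = 9.51-fold, so this part is minor.

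**Per-infusion denominator.** Six events in 48 first infusions give 12.5% at every cut-off. With m infusions per subject at equal risk, 6m/(48m) is again 12.5%.

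**The case against.** The strongest reply is that the SAP already reports these events on stable scales. Section 3.8.2 with Appendices 2 and 3 gives number and percentage for each targeted event at 75 ± 5 and 365 ± 14 days after the initial and final infusion. Appendix 5, laid out like Appendix 4, gives number and percentage of patients for all adverse events, targeted or not. Sections 3.8.2.1 and 3.8.2.2 compare the initial with the final infusion by McNemar's test within subjects who had more than one. Appendix 4 prints the event count beside each rate and has one row per event, so the combined column does not merge different complications. Section 3.8 promises separate tables by attribution.

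All of this stands, and it limits the point. A reader might infer that procedural safety is reported nowhere else on a sound scale, or that extra risk from a repeat infusion cannot be seen anywhere in the SAP. The documents support neither inference: both hold only for Appendix 4 taken alone. A reader might also take tenfold as the expected distortion. It is the upper end for the chosen cut-offs, and it needs one infusion per subject.

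The reply does not remove the flaw. The SAP still commits to printing a rate and an interval for procedure-related events in Appendix 4, and no other table corrects those numbers or counts events per infusion performed.

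**Conclusion.** The point holds and is minor. For events that arise only around an infusion, the rate and interval in Appendix 4 depend mainly on length of follow-up. Between the illustrative cut-offs of Day 75 and Day 730 the rate falls about 9.7-fold with one infusion per subject and about 5- to 3-fold with a mean of two to three, at unchanged risk per infusion. These figures assume complete follow-up, equal risk at each infusion, events close to the infusion, and only the first infusion before Day 75. The six events are the SAP's template example; the fold changes do not depend on that count.

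The distortion is limited to the rates and intervals in Appendix 4. These tables are descriptive. The SAP ties no decision to them, and section 4.2 refers to the protocol for the suspension criteria. It would go too far to say that the trial's safety reporting as a whole is unsound.

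**What to change.** In section 3.8.3 and Appendix 4:

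- Split the related column by the attribution already recorded. Section 3.8.1 treats procedure and islet product together as islet transplantation, so state whether the procedure can be separated in the record or whether the new column covers both.
- For events attributed to the transplant procedure, replace the person-day rate with number and percentage per infusion performed, shown for first, second and third infusions, with an exact interval.
- Assign each event to the most recent infusion. List late-appearing events rather than cutting them off at Day 75; the wound-complication category in section 3.8.2, for instance, includes later hernia.
- State that events attributed to both the procedure and the immunosuppression appear in both columns.
- Keep person-day rates for immunosuppression-related and unrelated events.

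The cost is SAP wording and one more column group in Appendix 4. Attribution is already recorded (sections 3.8 and 3.8.1), and infusion dates are known because the visit schedule restarts at each transplant (section 3.1.2). The primary analysis is untouched. The downside is that procedure events will look less rare than on the person-day scale.

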2.1 Study Design

This is a prospective, single-arm, multi-center study in islet transplantation. The centers participating in this phase 3 study will also undertake separate, phase 2 studies in islet transplantation, using innovative manufacturing and/or immunosuppressive regimens. In order to avoid bias in selection of subjects for these studies, eligible subjects will be randomized, prior to transplantation, to participate either in the phase 3 or a site-specific phase 2 study. The participating centers will treat a total of 48 study subjects accrued over 24 months in this phase 3 study.

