Appendix 5 - Identification of Adverse Events at Month # since the Randomization

	AE related to the islet transplantation (islet product or islet transplant procedure) or immunosuppression and/or infection prophylaxis		AE not related to the islet transplantation (islet product or islet transplant procedure) or immunosuppression and/or infection prophylaxis	
All Adverse Events	Identification of incidences	Number and percentage of patients who have had the incidence	Identification of incidences	Number and percentage of patients who have had the incidence
Body System A 1. Grade 5 2. Grade 4 Event 1 Event 2 ⋮ 3. Grade 3 Event 1 Event 2 ⋮ 4. Grade 2 Event 1 Event 2 ⋮ 5. Grade 1 Event 1 Event 2 ⋮	C111 C112 C113* C221 C231 C232 C331 C421 C461	6 (12.5%)		
Body System B 1. Grade 5 2. Grade 4 Event 1 Event 2 ⋮ 3. Grade 3 Event 1 Event 2 ⋮ 4. Grade 2 Event 1 Event 2 ⋮				

5. Grade 1 Event 1 Event 2 ⋮				
Body System C 1. Grade 5 2. Grade 4 Event 1 Event 2 ⋮ 3. Grade 3 Event 1 Event 2 ⋮ 4. Grade 2 Event 1 Event 2 ⋮ 5. Grade 1 Event 1 Event 2 ⋮				
⋮				

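### Adverse-event rates get large-sample likelihood intervals in a table where cells with few or no events are to be expected; exact Poisson limits should be named instead

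*SAP*

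**What the plan says.** SAP section 3.8.3 assumes that, for each subject, "the incidence of a particular event is a Poisson process with the homogeneous incidence rate" λ, expressed per 100 person-days. For a subject followed r days, "the incidence of this event is distributed according to the Poisson distribution with mean" rλ/100. The rate is estimated by maximum likelihood, and a "95% confidence interval derived using the maximum likelihood estimator theory will be also reported".

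The Appendix 4 shell has a column for the "confidence interval of λ based on MLE theory" twice, once for events related to the transplant or the immunosuppression and once for unrelated events. The rows run by body system, then severity grade, then individual event: "Any event that appears in a body system will be categorized into one of the five severity grades". Every body system in the shell has its own Grade 5 line. The trial is small: "The participating centers will treat a total of 48 study subjects" (section 2.1).

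No rule covers cells with zero or few events, and nothing allows for rates that differ between subjects. Elsewhere in the safety analyses, sections 3.8.2.1 and 3.8.2.2 use exact two-sided 95% intervals for immune sensitization, and section 3.8.2.2 does so for worsening retinopathy. The same sections pool severity grades when events are rare, but only for the McNemar comparisons.

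**The concern.** Intervals from maximum likelihood theory rest on a large-sample approximation, and Appendix 4 divides about 48 subjects' events so finely that the approximation will often have little to work with. A body system with no deaths would show a rate of zero with an interval of no width, which reads as certainty that the risk is nil. An event seen only as related would show the same in the unrelated column. For rare serious events the upper limit is the figure a reader needs, and on the ordinary reading the recipe sets it too low.

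Safety is part of the primary objective (section 2.2.1). The Appendix 4 title leaves the month open, so the table can also be produced early, when counts are smallest.

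A second and separate weakness is the common rate. If some subjects are more prone to an event than others, the Poisson variance is too small on any likelihood scale.

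**Working it through.** **The plan's own figure.** Section 3.8.3 states no rate or interval. The nearest figure is the Appendix 5 illustration: its codes name 6 distinct patients, and 6/48 = 12.5%, as printed.

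**Inputs.** The Poisson model and interval method come from section 3.8.3 and Appendix 4, and the 48 subjects from section 2.1. Follow-up for this table is not fixed. I assume 48 × 365 = 17,520 person-days, and 48 × 730 = 35,040 for the range. Results in events do not depend on this choice.

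**Formulas.** Let x be the number of events and T the person-time in units of 100 person-days.
- Estimate: x/T. Its standard error from Fisher information: √x/T.
- Ordinary interval, in events: x ± 1.96√x.
- Exact (Garwood) interval, in events: χ²(0.025; 2x)/2 to χ²(0.975; 2x + 2)/2, with lower limit 0 at x = 0.
- Log-scale interval: x·exp(±1.96/√x).
- Likelihood-ratio interval: all m with 2[x·ln(x/m) − (x − m)] ≤ 3.84.

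**Results, in events.**

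| x | Ordinary | Exact | Likelihood ratio | Log scale |
|---|---|---|---|---|
| 0 | 0 to 0 | 0 to 3.69 | 0 to 1.92 | undefined |
| 1 | −0.96 to 2.96 | 0.03 to 5.57 | 0.06 to 4.40 | 0.14 to 7.10 |
| 2 | −0.77 to 4.77 | 0.24 to 7.22 | 0.33 to 6.18 | 0.50 to 8.00 |
| 3 | −0.39 to 6.39 | 0.62 to 8.77 | 0.75 to 7.78 | 0.97 to 9.30 |
| 4 | 0.08 to 7.92 | 1.09 to 10.24 | 1.24 to 9.29 | 1.50 to 10.66 |

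The ordinary lower limit is negative when 0 < x < 1.96² = 3.84, so at 1, 2 and 3 events whatever the follow-up. The upper limit is 1 − 2.96/5.57 = 47% too low at one event and 1 − 6.39/8.77 = 27% too low at three.

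As a rate, the exact upper limit at zero events is 3.69/175.2 = 0.021 per 100 person-days at 17,520 person-days, and half that at 35,040. The ordinary interval reports 0.

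**Coverage of the nominal 95% ordinary interval when the Poisson model is true.** It is 39% at 0.5 expected events, 63% at 1, 86% at 2, 80% at 3, 87% at 5 and 93% at 10. At 0.5 the shortfall is essentially the chance of no events, exp(−0.5) = 61%, because the zero-width interval then misses.

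**Zero events on the likelihood-ratio scale.** The condition becomes 2m ≤ 3.84, so the limit is 1.92. With a true expected count just above that, zero events occur with probability exp(−1.92) = 15%, and the interval then misses.

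**Clustering.** In a simulation of 48 subjects with gamma-distributed rates (assumed variance 1 to 5 times the squared mean) and 20 expected events, coverage was 90% down to 73%, against 95% with a common rate.

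**The case against.** The strongest reply is that the SAP never prescribes estimate plus or minus 1.96 standard errors. A reader might infer that it does, but the text names no scale. Log-scale and likelihood-ratio intervals are also likelihood-based and cannot go negative, and on the log scale the upper limit is not understated once there is at least one event. This stands: the negative limits belong to the ordinary reading. It does not rescue the zero-event cell, where the log scale gives nothing and the likelihood-ratio limit is about half the exact one.

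The SAP also gives no expected event counts, and event rows appear only for events that occur. Sparse cells are therefore an expectation drawn from the layout. Zeros would arise mainly in the opposite attribution column and on the Grade 5 lines.

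Two further inferences are tempting and not supported. One is that any repeat event in a subject makes the limits too narrow. A Poisson process allows repeats, so only clustering beyond chance does this. The other is that the Appendix 5 codes, such as "C111 C112 C113", reveal how much clustering to expect. They are placeholders that explain a numbering convention, so they show only that repeats are counted.

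Finally, no hypothesis or threshold in the SAP depends on these limits. Section 3.7.2 confines hypotheses to the primary analyses, and sections 4.2.1 and 4.2.2 leave the suspension criteria to the protocol. That limits the consequence but does not make the limits right.

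**Conclusion.** The point holds as a badly chosen interval method for a descriptive safety table. On the ordinary reading the method fails at zero to three events: no width at zero, impossible lower limits at one to three, and upper limits 47% too low at one event and 27% too low at three. At zero events no likelihood scale gives an adequate limit. The conclusion rests on reading the phrase about likelihood theory in the usual way and on expecting sparse cells from the table's splits; only the per-100-person-day rates depend on the assumed follow-up.

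The clustering weakness is real in principle, but the SAP gives no data from which to size it; the simulated coverages rest on assumed variances. A reader might conclude that the trial's safety or efficacy findings are compromised. The SAP does not support that: the primary efficacy analysis does not use these intervals. The change is worth making because reported safety limits would differ at almost no cost.

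**What to change.** In section 3.8.3 and in both interval columns of Appendix 4, replace the reference to likelihood theory with exact (Garwood) Poisson limits for every cell: lower χ²(0.025; 2x)/(2T), set to 0 when x = 0, and upper χ²(0.975; 2x + 2)/(2T), with T in 100 person-days. This matches the exact intervals already used in sections 3.8.2.1 and 3.8.2.2.

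Exact Poisson limits still assume a common rate. So add to Appendix 5, which already tabulates the number and percentage of patients with each event, an exact (Clopper-Pearson) interval for that proportion. It counts each subject once and is unaffected by repeats. With no affected subjects among 48, for example, the upper limit is 1 − 0.025^(1/48) = 7.4%.

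A cell-by-cell switch to a robust variance or a negative binomial model whenever a subject has repeats is not advised. With three events all in one of 48 subjects, the subject-level standard error is 3.0 and the limits are 3 ± 1.96 × 3.0, or −2.9 to 8.9, negative again. With two events in one subject the standard error is 2.0, and the upper limit of 5.9 is below the exact 7.2. A negative binomial cannot be fitted reliably to one or two affected subjects, and data-driven switching makes rows hard to compare.

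The cost is a change of SAP wording, one added interval in a table shell, a few lines of code and somewhat wider intervals. No new data are needed.
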